This proposal involves two studies of evidence-based suicide prevention practices triggered by CareSource justice notifications, in a 2x2 factorial design. The **first study** will randomize CareSource's ~43,000 Ohio subscribers who pass through jails over 12 months to receive monthly Caring Contact letters sent by CareSource over a 6-month period or to Care as Usual. The **second study** (running simultaneously) will involve a subset of ~6,000 of the 43,000 subscribers passing through jail who were seen in one of 12 large BH agencies in the 6 months prior to jail detention. Using a stepped wedge design, the 12 agencies will be brought online over time, receiving (a) notifications of jail detentions/releases with instructions for re-engaging clients in services; and (b) training in the Safety Planning Intervention plus notification to use it when a subscriber with past *medically treated* suicide attempts (identified by CareSource through claims data) is released from jail.

Specifically, we plan to examine the following:

Aim 1: Evaluate the effectiveness of the implemented study interventions.

Hypothesis 1a: CareSource subscribers who receive CC letters during the 6-month period will have fewer claims related to suicide attempts than subscribers who did not receive CC letters.

Hypothesis 1b: Provider involvement in the reports, re-engagement, and training (RRT) intervention will be associated with a reduction in subscriber claims related to suicide attempts. Further, the addition of flags and recommendations to provide SPI for individuals with past 12 months claims data identified suicide attempts will further reduce suicide attempts.

Aim 2. Examine the number of outpatient behavioral health claims in the 6 months following the index jail release and number of calls to CMS line as mediators of the intervention/s effects on suicide attempts. Mediation will be revealed by the extent to which the intervention effect parameter estimates change with the addition of the putative mediator. We will use bootstrap methods to estimate 95% uncertainty intervals around the mediated effect.

Aim 3. Examine intervention cost-effectiveness and return on investment. We will examine costs (and savings) in future years for both the Caring Contacts and Reports, Re-engagement, and Training (RRT) components of the proposed study.

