For Aim 1, we will assess total number of subsequent attempts using the already-developed Mental Health Research Network (MHRN) algorithm for extracting MT suicide attempt information from claims data.^{10-12,48-58} The main effectiveness analysis is planned as a comprehensive model (i.e., including all 43,000 subscribers) evaluating Study 1 and Study 2 intervention effects, which provides optimal power and the ability to test interactive effects of interventions. All analyses will covary baseline (i.e., past year) values of dependent variables, and will use days incarcerated in the 6 months after the index jail release as an offset. **MT suicide attempts.** The main analysis framework will be logistic regression with the cumulative risk of a claims-data-identified suicide attempts requiring medical treatment over six months post-release as the outcome. We will secondarily use a negative binomial model and a count outcome for the number of MT suicide attempts. Our models will include robust standard errors due to clustering at the agency level. We will adjust for study month, and include indicator variables reflecting: (1) Study 1 intervention condition (i.e., CC or CAU); (2) inclusion in Study 2; (3) Study 2 intervention condition (i.e., RRT or Control). The ***hypothesis that the Study 1 intervention (CC) reduces suicide attempts*** is evaluated with magnitude and significance of parameter estimate associated with random assignment to the Study 1 intervention. The ***hypothesis that the Study 2 intervention (RRT) reduces suicide attempts*** is tested with the parameter estimate associated with exposure to the level 2 intervention. ***The hypothesis that the addition of flags and recommendations to provide SPI*** for individuals with past 12 months claims data identified suicide attempts (one component of the Study 2 intervention) ***will further reduce suicide attempts*** will be tested through the interaction between past history of suicide attempt and being in the Study 2 intervention condition. Identical analyses will be conducted for the other outcomes (all count outcomes): all cause injury and poisoning, outpatient BH visits, calls to CMS line, suicide-related ED visits/hospitalizations, and returns to jail detention. ***Exploratory.*** We will evaluate the interaction of Study 1 and Study 2 interventions by including an interaction term of the two indicators. ***Moderators.*** We will test sex, race/ethnicity, past suicide attempt (y/n), past 6-month BH visit (y/n), past 12-month arrest (y/n), area Deprivation Index,⁵⁹⁻⁶⁰ Mental Health Professional Shortage Area (HPSA)

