
score,⁶¹⁻⁶² and per capita incarceration (by zip code) as moderators of intervention effects on suicide attempts, using $p < .01$.

Aim 2 will be analyzed by examining the number of outpatient BH claims in the 6 months following the index jail release and number of calls to the CMS line as mediators of the intervention/s effects on suicide attempts by adding this variable to our effectiveness model. Mediation is revealed by the extent to which the intervention effect parameter estimates change with the addition of the putative mediator. We will use bootstrap methods to estimate 95% uncertainty intervals around the mediated effect.

For Aim 3, our grants accounting will capture the costs of the CC mailings. Treatment received as part of the intervention and CAU conditions (including outpatient, inpatient, and ED mental health and suicide-related medical care visits) will be tracked using claims data. Costs of CAU will be computed as CareSource payments plus co-pay and deductibles. We will add training costs for providers but exclude other research costs that would not be incurred if RRT was standard care. The primary cost-effectiveness (CE) measure, computed from a societal perspective for each intervention arm, will be the program cost divided by the sum of suicide attempts prevented. We also will assess the net cost of the program from a MCO perspective. That measure will exclude patient payments from costs.

Costs (and savings) in future years will be discounted to present value in the year of jail release using the 3% discount rate recommended by the Second Panel on Cost-Effectiveness in Health and Medicine.⁶³ We will bootstrap the 95% uncertainty interval around the CE ratio. Analyses from the MCO perspective will compute the change in claims costs by running a generalized linear model (GLM) with gamma, inverse Gaussian, or Poisson variance based on data distribution, the log link function, and robust standard errors.⁶⁴ We will use a 2-part GLM unless less than 5% of patients have zero costs. Independent variables will include treatments received, demographics, Elixhauser co-morbidities,⁶⁵ and days of MCO coverage after jail discharge. We also will track the MCO separation rate post-discharge by group.

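### The Aim 2 mediation model has no term for days of CareSource coverage, so loss of coverage biases the visit–attempt link upward and understates mediation through outpatient visits

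*Combined protocol and SAP*

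**What the plan says.** Section 2.A (Aim 2) and the Aim 2 paragraph of section C4, Data Analysis, name two mediators. C4 plans to analyse Aim 2 by "examining the number of outpatient BH claims in the 6 months following the index jail release", together with a count of CMS-line calls. They are to be tested "by adding this variable to our effectiveness model", and the criterion is a change in coefficient: "Mediation is revealed by the extent to which the intervention effect parameter estimates change with the addition of the putative mediator". Bootstrap 95% intervals are planned.

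The model that receives the mediator is the Aim 1 model in the same section: "The main analysis framework will be logistic regression with the cumulative risk of a claims-data-identified suicide attempts requiring medical treatment over six months". It adjusts for baseline values, study month and indicators of study condition, and it uses time in jail after the index release as an offset. It contains no covered-days term. C4 sets no continuous-coverage rule and no censoring when coverage ends; it says only that each subscriber is followed for six months through claims. The Study Outcomes paragraph of section C2 makes claims the source for all outcomes.

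The plan does expect coverage to vary. The Aim 3 cost model includes "days of MCO coverage after jail discharge", and the plan adds: "We also will track the MCO separation rate post-discharge by group". Neither is carried into Aim 2. No separation rate is given.

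**The concern.** Someone who leaves CareSource after one month can show few visits and has little chance of an observed attempt. Someone covered throughout has more opportunity for both. Covered time is thus a common cause of the observed mediator and the observed outcome, and the model does not hold it fixed. The visit–attempt association is shifted toward more visits, more attempts. A protective effect of visits is then partly cancelled, and the intervention coefficient moves less than it should when the count is added.

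This does not require retention to differ between arms. The days-incarcerated offset cannot remove it, because time in jail does not measure coverage. Bootstrap intervals would be centred on the biased value.

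At stake is the mechanism claim. The RRT Fidelity paragraph in section C2 says outreach cannot be tracked at scale for the 6,000 Study 2 subscribers, and it relies on the service-engagement analysis to trace the path from reports to services to attempts.

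**Working it through.** The plan gives no figure for Aim 2, so there is none to reproduce.

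**Inputs from the documents.** Six-month attempt risk 0.05; 43,000 subscribers, 1:1; risks of 0.034 and 0.204 without and with a past-year attempt, about 10% with one (all from the Statistical power paragraph of C4).

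**Assumed inputs.** A share s loses coverage, at a time uniform over the six months, equally in both arms and unrelated to risk. Visit distributions and visit effects are as stated below. The mediated effect is the intervention log-odds coefficient without the mediator minus that with it; negative means protective mediation.

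**Direction, by algebra.** Let f be the fraction of the six months covered. Then E(f) = 1 − s/2, E(f²) = 1 − 2s/3 and Var(f) = s/3 − s²/4. With no true visit effect, observed visits have mean μf and an attempt is observed with probability pf, so their covariance is μ·p·Var(f). This is positive whenever s > 0.

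- s = 10%: Var(f) = 0.0333 − 0.0025 = 0.0308
- s = 20%: 0.0667 − 0.0100 = 0.0567
- s = 30%: 0.1000 − 0.0225 = 0.0775

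Worked case at s = 10%, μ = 6, gamma–Poisson visits (shape 1), p = 0.05:

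- Covariance = 6 × 0.05 × 0.0308 = 0.00925.
- Variance of observed visits = 6 × 0.95 + 36 × (2 × 0.9333 − 0.95²) = 40.4.
- Observed risk = 0.05 × 0.95 = 0.0475.
- False slope ≈ 0.00925 / (40.4 × 0.0475 × 0.9525) = +0.005 per visit.
- If the intervention adds 20% more visits (1.2 × 0.95 = 1.14 observed), the false mediated effect ≈ 1.14 × 0.005 = +0.006.

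Simulation agrees: slope +0.0049, mediated effect +0.006.

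**Size with a true link.** Simulation of 2,000,000 subscribers per setting: mean 6 visits, 20% more with the intervention, logit = −2.8 − 0.03 × visits − 0.08 × arm.

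| Loss | Full data | Planned model | Recovered |
|---|---|---|---|
| 5% | −0.0303 | −0.0270 | 89% |
| 10% | −0.0296 | −0.0234 | 79% |
| 20% | −0.0291 | −0.0173 | 59% |
| 30% | −0.0300 | −0.0129 | 43% |

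With no true visit effect, the planned model gives +0.006, +0.010 and +0.014 at 10, 20 and 30% loss.

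**Sensitivity to the assumptions.** A separate simulation used the plan's 0.034/0.204 risks, mean 4 visits and 25% more visits with the intervention. Share of the mediated effect kept by the planned model:

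| True log-odds per visit | 10% loss | 20% | 30% | 50% |
|---|---|---|---|---|
| −0.15 | 89% | 80% | 71% | 56% |
| −0.05 | 82% | 64% | 50% | 22% |
| −0.02 | 61% | 33% | about 0 | sign reversed |

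**Which element is at fault.** In a repeat of the mean-6 simulation, the observed count was kept and only log(coverage) was added to both models. At 5, 10, 20 and 30% loss the mediated effect was −0.0301, −0.0296, −0.0295 and −0.0296, against −0.0303, −0.0300, −0.0301 and −0.0310 in full data: 99, 99, 98 and 95%. Using visits per covered time as well gave −0.0302, −0.0297, −0.0298 and −0.0301. The missing coverage term is the defect; converting to a rate adds almost nothing. Restricting to fully covered subscribers recovered about 100%.

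**The case against.** Several stronger readings are tempting, and the documents do not support them.

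- **That raw counts are themselves the fault.** They are not: the count works nearly as well as the rate once coverage is in the model. A rate can also be unstable for people covered only a few days. The gap starts in the Aim 1 model, and Aim 2 inherits it.
- **That the plan will hide true mediation.** In the mean-6 simulation, with standard errors scaled to 43,000, the visit coefficient stays clearly protective: −0.0237 (SE 0.0039) at 10% loss, −0.0190 (0.0040) at 20% and −0.0143 (0.0041) at 30%. Against a total effect of about −0.10, the mediated share falls from about 29% to 23% at 10% loss and 18% at 20%. That is understatement.
- **That a false link is sure to appear when there is none.** At 10% loss the false slope is +0.0049 (SE 0.0030), about 1.6 standard errors, and about one standard error in the mean-4 simulation. It becomes material near 20% loss or more.
- **That CMS-line calls are affected in the same way.** The simulations cover visits only, and the documents do not say whether calls stop being recorded when coverage ends.

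It is also fair to say that every size here rests on a separation rate, visit distribution and visit effect that the documents do not give; that the remedy was tested only with loss unrelated to arm or risk; and that Aim 2 is explanatory, with the Aim 1 estimate not at issue here. All of this stands and limits the size of the point. It does not remove the gap or change its direction: in every simulated setting with coverage loss the mediated effect moved toward zero or past it, and with no loss there was no false link.

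**Conclusion.** The point holds as a systematic bias of known direction and unknown size. As written, Aim 2 lets covered time act on both the visit count and the observed outcome without adjustment, and so understates mediation through outpatient visits. Under the assumed inputs about 80% of the mediated change is recovered at 10% loss, 60% at 20% and 40–45% at 30%. If few subscribers leave within six months, the error is minor. If loss is high or the true visit effect is weak, mediation could be missed or appear with the wrong sign. These figures assume uniform exit times and loss unrelated to arm or risk; informative loss was not simulated and could change the size. The change should be made before analysis, because the bias is avoidable with a variable the plan already needs.

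**What to change.** In the Aim 2 paragraph of C4:

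1. Add log(days of MCO coverage within the six-month window) to both the model without and the model with the mediator. Give a rule for anyone with zero covered days, for whom the log is undefined.
2. State how this term combines with the days-incarcerated offset.
3. Repeat the analysis in subscribers covered for the full six months, as a sensitivity analysis.
4. State whether CMS-line calls stop being recorded when coverage ends; if they do, treat them in the same way.
5. Report the separation rate by group, already tracked for Aim 3, beside the mediation result.

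Expressing visits per covered day is optional.

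The cost is a few sentences, since covered days are already needed for Aim 3. The drawback is that coverage is measured after randomisation: neither the adjusted nor the full-coverage analysis fully removes bias if loss of coverage depends on arm or risk, so both should be reported with that caveat.

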Following notification of jail release, CareSource will mail CC letters to subscribers randomized to CC (~21,500) monthly for 6 months after jail release. CC involves sending individuals at risk for suicide brief, non-demanding messages of care.^{26,34,45,46} Messages: (1) include a simple expression of care or concern; (2) are non-demanding; and (3) include a reminder of available resources/ways to connect with care. CCs in this study will be addressed from and refer to CareSource's Care Management team via the care management service (CMS) line. This team, who works with individuals to arrange appointments with appropriate providers and other relevant resources (including crisis lines). Individuals who are re-arrested during the 6-month follow-up period will continue to receive letters, but will not be re-randomized.

Caring Contacts fidelity: CC letters sent, the dates they were sent, and any letters returned will be tracked using CareSource's automated mailing system. Since the mailing system is automated, it should involve minimal human error or noncompliance.

Study 2: Reports, re-engagement, and training (RRT)

RRT Intervention will involve 120 BH providers who provide services at 12 of the largest BH agencies in Ohio (10 providers per agency). These agencies serve ~6,000 of the 43,000 CareSource subscribers who passed through jail in the 6 months prior to detention. Providers who consent to participate in the RRT Intervention will receive: (a) notifications of jail release for their clients, (b) instructions for re-engaging these clients in services and training in suicide risk assessment to use at re-engagement; and (c) training in SPI plus notification to use SPI when a client with past suicide attempts is released from jail. Suicide attempts for this proposal will primarily refer to medically-treated (MT) suicide attempts (i.e., presented

to ED/hospital for treatment following a suicide attempt) as these are the only types of attempts we can identify through claims data.

Site Interviews: The primary contacts at each of the participating BH agencies will participate in the site interviews. These will be conducted virtually and will be recorded. Audio/video files recorded during the meeting will be downloaded onto secure servers at Butler and Michigan State University (MSU).

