RRT Fidelity. We will be able to electronically track whether reports go out and whether they are timely/accurate. In addition, although we do not have a scalable way to track outreach attempts for 6,000 subscribers in Study 2, we will carefully document implementation processes and meet monthly with CareSource and intervention agencies, hear their experiences, offer feedback, and help problem-solve challenges. We will keep structured implementation process notes from these meetings for further analysis. Provider names will be included in the notes. All data from the implementation process feedback will be securely stored in REDCap. No names or identifiers will be used in any published works and will be accessible only to authorized research staff. Testing our service engagement mechanism will also help to elucidate steps in the causal chain (i.e., from the reports, to services provided, to suicide attempts).

Assignment to “intervention” and “control” conditions in the two studies is independent: participants may receive Intervention-Intervention, Intervention-Control, Control-Intervention, or Control-Control. Participants will be followed for 6 months following jail release using claims data.

C4. Data Analysis

Twelve months of historical (i.e., prior to arrest) and six months of prospective (i.e., after release) jail and Medicaid claims data will be extracted from CareSource’s Jail-Medicaid database for each participating subscriber for all measures, including demographics, diagnoses, suicide attempts, service use, number of arrests, dates of jail bookings/releases, and days incarcerated. Each eligible subscriber will be followed for 6 months following the index release from jail using claims data. CareSource will provide a limited dataset to the P50 Center (at MSU) that will be de-identified and analyzed by Center statisticians. Because these statisticians are employed by Brown University, an IAA will be established with both MSU and Brown University.

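### Aim 2 counts visits and calls over the same six months as attempts with no ordering rule, so the mediated effect can be biased in either direction, by an unknown amount.

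*Combined protocol and SAP*

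**What the plan says.** In the Data Analysis section (C4), Aim 2 adds to the effectiveness model "the number of outpatient BH claims in the 6 months following the index jail release and number of calls to the CMS line". The Specific Aims repeat this. The decision rule is: "Mediation is revealed by the extent to which the intervention effect parameter estimates change with the addition of the putative mediator". A bootstrap 95% interval accompanies the estimate.

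The model being extended is the Aim 1 logistic regression, which takes the cumulative risk of a medically treated attempt "over six months post-release as the outcome". All analyses also "will use days incarcerated in the 6 months after the index jail release as an offset".

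The calls have no window of their own. The same six months is an inference from C4, where, for all measures, "six months of prospective (i.e., after release) jail and Medicaid claims data will be extracted".

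The RRT Fidelity paragraph says that testing service engagement will help to "elucidate steps in the causal chain (i.e., from the reports, to services provided, to suicide attempts". That is an ordered chain, but it is stated as a goal. No section sets a lag, a landmark, a time-varying mediator or an exclusion of contacts after an attempt.

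**The concern.** A mediator has to come before the outcome that it is meant to explain. A six-month total of visits and calls mixes contacts before an attempt with contacts after it, and the planned model cannot separate them.

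Two conditions turn this into bias: an attempt must change later contacts, and contacts must differ by arm. Both are plausible here. Counted attempts are those that came "to ED/hospital for treatment following a suicide attempt", so outpatient follow-up may rise afterwards. It may also fall, through admission, return to jail or loss of coverage. The plan lists suicide-related hospitalizations and returns to jail among its outcomes and tracks separation from the MCO. As for the second condition, the letters "include a reminder of available resources/ways to connect with care", and RRT trains providers to re-engage clients, so both interventions aim to raise contact with care.

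Aim 2 is the planned test of the service-engagement mechanism. A biased answer could lead readers to reject a mechanism that works or to credit one that does not.

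**Working it through.** **Plan's own figure.** The documents give no visit rate, call rate, mediated share or power for Aim 2, so there is nothing to reproduce. What follows shows direction and scale under stated assumptions.

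**Inputs from the protocol (Statistical power; Training behavioral health providers).** 43,000 subscribers, 1:1 to letters; 6,000 in Study 2; about 10% with a past attempt; six-month risk .034 without and .204 with a past attempt; 12 agencies starting at Months 4, 6, 8 and 10.

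**Assumed.** Control mean m = 2, 4 or 8 outpatient visits in six months; person-level gamma (shape 1)-Poisson variation, so the variance is m + m²; 20% more visits under intervention; k extra visits after an attempt. The incarceration offset is not modelled.

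**Measure.** Shift = intervention log-odds without the mediator minus log-odds with it. Mediation of a protective effect gives a negative shift.

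**Step 1: closed form, inert visits (true shift 0).** If people with an attempt have k extra visits, the mediator's coefficient is roughly k / Var(M). Adding the mediator then moves the intervention coefficient by that amount times the arm difference d in mean visits:

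shift ≈ d × k / Var(M)

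Var(M) is the average of the two arms' variances.

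| m | d = 0.2m | Var(M) | k = 1 | k = 3 |
|---|---|---|---|---|
| 2 | 0.4 | (6 + 8.16)/2 = 7.08 | +0.056 | +0.169 |
| 4 | 0.8 | (20 + 27.84)/2 = 23.92 | +0.033 | +0.100 |
| 8 | 1.6 | (72 + 101.76)/2 = 86.88 | +0.018 | +0.055 |

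Simulation of the planned with/without comparison at N = 43,000 gives about +0.06/+0.03/+0.02 for k = 1 and +0.17/+0.10/+0.055 for k = 3. The formula also shows that the shift vanishes if k = 0 or d = 0. With no arm difference and a direct effect of ln 0.89, the simulated shift was +0.001 to +0.002.

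**Step 2: the opposite direction.** Halving visits after an attempt makes k negative. In simulation the shift is about -0.03/-0.03/-0.035 for m = 2/4/8: apparent mediation by visits that do nothing.

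**Step 3: true mediation.** A separate simulation used other assumptions: 0.5 visits per month, 30% more under intervention, total OR about 0.89, and a true indirect log OR of about -0.058. Visits after an attempt were multiplied by a factor.

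| Factor | Planned estimator |
|---|---|
| 0.5 | -0.247 |
| 0.8 | -0.134 |
| 1.0 | -0.060 |
| 1.1 | -0.021 |
| 1.15 | -0.004 |
| 1.2 | +0.018 |
| 1.5 | +0.131 |

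A person-month model using only visits before the attempt gave -0.057 to -0.060 for every factor from 0 to 3. Simply stopping the count at the attempt gave about -0.42, because people with an attempt then have less time to accrue visits.

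**Step 4: RRT.** C4 plans one model of all 43,000, so the mediator's slope comes from everyone. Assume the same mean visits in the other 43,000 - 6,000 = 37,000. Most subscribers are then unexposed to RRT and Var(M) is close to m + m². With inert visits and a 20% difference, k = 1 gives 0.8/20 = +0.04 (m = 4) and 1.6/72 = +0.02 (m = 8). Simulation with the stepped wedge, study month and ICC .01 gives about +0.04/+0.02 (sampling SD 0.015/0.01) for k = 1 and +0.13/+0.07 (SD 0.05/0.03) for k = 3, or about 2 to 2.5 SDs. At a 5% arm difference the shift is within one SD in most settings.

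**Step 5: the interval.** Bootstrap resampling repeats the same unordered count, so it describes sampling error around the biased quantity.

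**The case against.** The strongest reply is that the harm is hypothetical. Aim 2 is secondary, no document gives a visit rate or says how contacts change after an attempt, and a 20% rise in visits from letters is unsupported. This stands as far as size is concerned: the figures above are illustrations, and a small arm difference gives a small shift. It does not answer the structural point, because the plan's rule gives a biased estimate whenever both conditions hold, and raising contact is what the interventions are for.

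A second reply is that emergency or hospital treatment of an attempt is not an outpatient claim; the plan lists it as a separate outcome. This also stands. Only later outpatient visits or calls can enter the mediator, so contamination is possible rather than automatic.

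A third reply is that a time-ordered model loses events and leaves confounding by severity. Both are true. In a simulation where severity drove both visits and attempts (inert visits, mean 4, 20% difference), ordered models still showed a false +0.019 to +0.021, or +0.008 to +0.009 after adjusting for past-year visits. The planned model gave +0.05 and +0.09 with one and three extra visits. Ordering therefore helps but does not make the result causal.

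A reader might infer that the overlap always hides mediation. The documents do not support that: they do not say whether outpatient contact rises or falls after an attempt, and a fall reverses the bias. A reader might also infer that overlapping windows are enough to bias the estimate. Step 3 at factor 1.0 shows otherwise.

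**Conclusion.** The concern holds as a missing ordering rule with consequences. As written, Aim 2 can attenuate, hide or reverse true mediation, or overstate or fabricate it, depending on how contacts change after an attempt. The bias needs two things, an effect of attempts on later contacts and an arm difference in contacts; without either it is essentially nil. Confidence is high that the rule is absent and that the mechanism operates under these conditions. Neither the direction nor the size in this trial can be known from the documents. The illustrative shifts rest on assumed visit distributions, arm differences and post-attempt changes.

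A reader might go further and doubt the main effectiveness results. The documents give no ground for that on this point: the mediator enters only the Aim 2 model, so the Aim 1 estimates are unaffected.

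**What to change.** In the Specific Aims (Aim 2) and C4, replace the full-window count with a prespecified time-ordered mediator. Either form would do:

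- person-months up to the first attempt, with visits and calls counted only through the previous month; or
- visits and calls in an early fixed window, with attempts analysed after that landmark among subscribers attempt-free at it.

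In either form:

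- Fit the models with and without the mediator on the same risk set.
- Adjust for past-year visits and past attempts, which the twelve historical months supply.
- Define time at risk per period, because the incarceration offset is written for the whole six months.
- State a window for the calls.
- Do not merely stop counting at the attempt, which creates a new artefact (Step 3).
- Keep the full-window model at most as a sensitivity analysis.
- State that confounding by severity remains, so the result is associational.

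**Cost.** This is wording and programming, with three downsides.

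1. Fewer attempts are analysed. At the planned 5% risk there are 0.05 × 43,000 = 2,150. If they are evenly spread, a one-month lag loses one sixth (leaving about 1,790) and a 2-month landmark one third (leaving about 1,430). If attempts cluster soon after release, the losses are larger.
2. The Aim 2 outcome no longer matches Aim 1's six-month risk.
3. Analysts need the order of visits, calls and attempts for each person. The Outcome analysis paragraph (Subject Population) says that shifted dates will still allow time ranges, whereas the Data Safety Monitoring Plan describes an analytic dataset aggregated to clinic level. These must be reconciled before extraction, with confirmation that each person's dates are shifted together and that call dates exist.
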